#### **2.4.6 Analyses of pharmacokinetic variables**

SAR425899 plasma concentrations of patients in the SAR425899 treatment groups will be listed and summarized by visit and time window and by antibody status in the PK population, using descriptive statistics by N, geometric mean, coefficient of variation, median, minimum and maximum.

Population PK modeling and simulation results would be provided in a separate report.

#### **2.4.7 Analyses of pharmacodynamics biomarkers**

Descriptive statistics (number, mean, standard deviation, median, minimum, and maximum) will be provided by treatment for pharmacodynamics biomarkers at the scheduled visits.

#### **2.4.8 Analyses of NASH and cardiovascular biomarkers**

Descriptive statistics (number, mean, standard deviation, median, minimum, and maximum) will be provided by treatment for NASH and cardiovascular biomarkers at the scheduled visits. GGT, ALT, and AST will be analyzed according to [Section 2.4.5.4](#), no additional analyses will be provided.

#### **2.4.9 Analyses of patient reported outcomes (health-related quality of life/health economics variables)**

##### **2.4.9.1 Analysis of PRO questionnaires (WRSM, APPDL and IW-SP)**

Descriptive statistics (number, mean, standard deviation, median, minimum, and maximum) will be provided by treatment for PRO questionnaires (WRSM, APPDL and IW-SP) at the scheduled visits.

PRO questionnaires (WRSM, APPDL and IW-SP) at Week 26 will be analyzed using the same ANCOVA model with missing post baseline values imputed by placebo control-based MI method as described in [Section 2.4.4.1](#) to compare each SAR425899 dose group with placebo. For missing value at baseline, missing data will be imputed using the same MI under the MAR assumption as described in [Section 2.4.4.1](#). The model will include fixed effect terms of treatment groups (SAR425899 0.12 mg, SAR425899 0.16 mg, SAR425899 0.20 mg, placebo and liraglutide), randomization strata of screening HbA1c value ( $<8$ ,  $\geq 8\%$ ), randomization strata of Visit 4 (Day 1) BMI ( $<35.0$  kg/m^2,  $\geq 35.0$  kg/m^2), and country, and the covariate of baseline value. Means and adjusted means of each treatment group will be provided, as well as adjusted mean and associated two-sided 95% CI of the differences between each SAR425899 dose group and placebo. The analyses include values at baseline and Week 26 (observed or imputed) regardless of treatment discontinuation or initiation of rescue therapy.

### **2.4.9.2 Analysis of the patient qualitative assessment of the treatment**

Patients' answers to the 3 open-ended questions will be analyzed qualitatively using qualitative data analysis software. This qualitative thematic analysis of patients answers will be based on grounded theory methods and involve creating codes corresponding to concepts and sub-concepts identified in the text. A global synthesis will establish the most relevant concepts reported by the patients (benefits, disadvantages and reasons to continue or not the drug). Additional descriptive statistics will be provided on the closed-ended questions. The analyses method for this exploratory analysis will be provided in a separate SAP and the analyses results will be documented in a separate report.

## **2.5 DATA HANDLING CONVENTIONS**

### **2.5.1 General conventions**

The following formulas will be used for computation of parameters.

#### **Renal function formulas**

The estimated glomerular filtration rate (GFR) will be calculated by 4 variable MDRD formula using the serum creatinine, race, age, and gender of the patient:

Standard unit:  $eGFR \text{ (mL/min/1.73 m}^2\text{)} = 175 \times [\text{Serum Creatinine } (\mu\text{mol/L)/88.4}]^{-1.154} \times \text{Age (year)}^{-0.203} \times 1.212 \text{ (if Black)} \times 0.742 \text{ (if female)}$

Conventional unit:  $GFR \text{ (mL/min/1.73 m}^2\text{)} = 175 \times \text{serum creatinine (mg/dL)}^{-1.154} \times \text{age (yr)}^{-0.203} \times 1.212 \text{ [if black]} \times 0.742 \text{ [if female]}$

#### **Urine albumin/creatinine ratio:**

Standard unit:  $\text{Urine albumin/creatinine ratio (mg/g)} = \text{Urine Albumin (mg/dL)} / [\text{Urine Creatinine (mmol/L)} \times 11.31] \times 1000$

Conventional unit:  $\text{Urine albumin/creatinine ratio (mg/g)} = \text{Urine Albumin (mg/dL)} / \text{Urine Creatinine (mg/dL)} \times 1000$

#### **Calculation of LDL-C**

When triglycerides is lower than or equal to 4.52 mmol/L (400 mg/dL), LDL-C is calculated using the Friedewald equation as:

Standard unit (mmol/L):  $\text{total cholesterol} - \text{HDL-C} - \text{triglycerides}/2.17$ ;

Conventional unit (mg/dL):  $\text{total cholesterol} - \text{HDL-C} - \text{triglyceride} /5$ .

When triglycerides is greater than 4.52 mmol/L (400 mg/dL), the Friedewald equation can not be used to derive LDL-C value, and the value of LDL-C will be considered as missing.

### ***Linked adverse events that worsened or became serious***

An AE that worsened or became serious will have a separate record in the data from the original event record with an AE identification number that links the new record to the original record. An AE that worsened or became serious will be considered a new recurring AE in the summary of recurrent events or in the summary of events by time intervals.

### **2.5.2 Data handling conventions for secondary efficacy variables**

All continuous secondary efficacy endpoints at Week 26 will be analyzed using an ANCOVA model as described in [Section 2.4.4.2](#). The analyses include all observed values at baseline and Week 26 regardless of treatment discontinuation or initiation of rescue therapy. Missing values will be imputed by control-based multiple imputation method under the missing not at random frame work.

For the categorical secondary efficacy endpoints, data handling conventions are described in [Section 2.4.4.2](#).

### **2.5.3 Missing data**

For categorical variables, patients with missing data are not included in calculations of percentages unless otherwise specified. When relevant, the number of patients with missing data is presented.

Derived variables will be considered missing if any of the original variables required to calculate them are missing. For example, if either a baseline assessment or an endpoint assessment is missing for a particular patient, then change from baseline at endpoint will be missing. Depending upon the assessment, analyses may not include all patients in the analysis population, because certain patients in the intended population may have missing data.

### ***Incomplete date of first injection***

Date/time of first injection is the first non-missing start date/time of IMP completed in the eCRF “Dosing(SAR425899/Placebo)” or “Dosing(Liraglutide)” module .

For patients who are randomized and dispensed a treatment kit but who are lost to follow-up just after Visit 4 (only the treatment kit number is reported in the eCRF dosing module without any dose information), the date of first injection will be imputed using the Visit 4 date. When a patient is randomized but not dispensed a treatment kit, the dosing module should be blank. In this case, the patient will be considered as randomized but not treated, “Not Taken” should be ticked in the e-CRF dosing module.

### ***Handling of computation of treatment duration if IMP end of treatment date is missing***

For the calculation of the treatment duration, the date of the last injection of IMP is equal to the date of last administration reported on the eCRF “Treatment Status” page. If this date is missing, the exposure duration should be kept as missing.

The last dose intake should be clearly identified in the eCRF and should not be approximated by the last returned package date.

### ***Handling of medication missing/partial dates***

No imputation of medication start/end dates or times will be performed. If a medication date or time is missing or partially missing and it cannot be determined whether it was taken prior or concomitantly, it will be considered a prior, concomitant, and post-treatment medication.

### ***Handling of missing data for categorical secondary efficacy endpoints***

Please see [Section 2.4.4.2](#).

### ***Handling of missing data for continuous efficacy endpoints***

Please see [Section 2.4.4.1](#) and [Section 2.4.4.2](#).

### ***Handling of missing data in the calculation of average 7-point SMPG***

In order to account for the situation that a patient could have SMPG at bedtime after 12 midnight, a day interval is defined for the study as 2:01 am-2:00 am the next day. All the SMPG measurements taken during the interval will be considered as measurements of the day. If there are more than one measurement for a time-point of a day, the average value will be used instead.

Only glucose measurements taken after the previous visit with scheduled 7-point SMPG measurements, and within a week of the next visit with scheduled 7-point SMPG measurements will be used to choose a SMPG profile for a patient and a visit. A patient has to have value for at least 4 time-points during a day interval for the SMPG profile to be considered as a complete profile. The day with a complete profile and the most glucose measurements (in terms of time-points) will be chosen as the SMPG profile for the patient and the visit. If there are more than one days with the most glucose measurements, the profile from the day closer to the next visit with scheduled 7-point SMPG measurements will be chosen.

For SMPG by time-point analysis, a similar principal will be applied in selecting the data for analysis. A glucose measurement for the time-point taken after previous visit with scheduled 7-point SMPG measurements, and closest to the next visit with scheduled 7-point SMPG measurements will be selected for the by time-point analysis.

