9.2.1.2.3 Self-monitored plasma glucose profiles

The 7-point SMPG profile should be measured at the following 7 points: preprandial and 2 hours postprandial for breakfast, lunch, dinner and at bedtime. Two hours postprandial (breakfast, lunch and dinner) is defined as 2 hours after the start of the meal.

The patients are requested to perform 7-point SMPG profile measurement over a single 24-hour period in the week before Visit 4 (Week 0), Visit 10 (Week 14), and Visit 12 (Week 26, end of treatment assessment visit). All SMPG values measured on these days will be recorded with a glucometer provided by the Sponsor.

9.2.1.2.4 *Body weight*

Body weight should be obtained with the patient wearing undergarments or very light clothing and no shoes, and with an empty bladder in fasting conditions, in the morning before breakfast. The same scale should be used throughout the study, and calibrated on a regular basis as recommended by the manufacturer. The use of balance scales is recommended; if digital scales are used, testing with standard weights is of particular importance. The floor surface on which the scale rests must be hard and should not be carpeted or covered with other soft material. The scale should be balanced with both weights at zero and the balance bar aligned. The patient should stand in the center of the platform as standing off-center may affect measurement. The weights are moved until the beam balances (the arrows are aligned). The weight is read and recorded in the eCRF and source data. Self-reported weights are not acceptable; patients must not read the scales themselves.

Body weight will be measured on days indicated in the flow chart (see [Section 1.2](#)). Weight should be measured in the fasting state in the morning at approximately the same time with an empty bladder, without shoes and only wearing undergarments or light clothing. Weight measured at screening Visit 1 will be used only for calculation of screening BMI for eligibility criteria whereas weight measured at Visit 4 will be used as baseline for assessment of change in body weight and for calculation of baseline BMI which will be the BMI value used for stratification.

9.2.1.2.5 *Blood glucose, insulin, and C-peptide*

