### **2.1.3.2 Secondary efficacy endpoint(s)**

#### **Continuous secondary efficacy endpoints**

The continuous secondary efficacy endpoints are:

- Change in body weight from baseline to Week 26,
- Change in FPG from baseline to Week 26,
- Change in 7-point SMPG profiles from baseline to Week 26 (each time point and average daily value),
- Change in PPG and in blood glucose excursion in response to a standardized meal test in up to 50% subset of all patients from baseline to Week 26 at time points premeal, 10 min, 20 min, 0.5 h, 1 h, 1.5 h, 2 h, 3 h, 4 h post meal,
- Change in fasting insulin, proinsulin, and C-peptide from baseline to Week 26,
- Change in insulin, proinsulin, and C-peptide and associated excursion values in response to a standardized meal test in up to 50% subset of all patients from baseline to Week 26 at time points premeal, 10 min, 20 min, 0.5 h, 1 h, 1.5 h, 2 h, 3 h, 4 h post meal,
- Change in HOMA- $\beta$  and HOMA-IR from baseline to Week 26,
- Change in lipid profile (total cholesterol, triglycerides, LDL-C, and HDL-C) and free fatty acids, and Ketone bodies from baseline to Week 26,

For 7-point SMPG profiles, the mean daily (ie, average on 7 points) change from baseline to Week 26 will be analyzed. In addition, the change from baseline to Week 26 for each of the 7 points will be evaluated, respectively.

For FPG, only values assessed in fasting condition will be analyzed.

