**Table 4 - Allocating an unscheduled measurement to a post-baseline visit**

Unscheduled measurement taken in study days a	Visit to be allocated to	Targeted study day for the visit
2 - 20	Visit 6 (Week2)	14
21 - 41	Visit 8 (Week 4)	28
42 - 76	Visit 9 (Week 8)	56
77 - 118	Visit 10 (Week 14)	98
119 - 160	Visit 11 (Week 20)	140
≥161	Visit 12 (Week 26)	182

a Study days are calculated from the day of first IMP injection; the day of first IMP injection is Day 1.

If more than one measurements are allocated to a visit, the one closest to the targeted study day (as shown in table above) will be used. Furthermore, if there are more than one measurement that are equally close to the targeted study day but measured on two different dates, measurements from the later date will be used. If there are more than one measurement taken on the same date, the average will be used.

The premature treatment discontinuation visit is entered in the eCRF if a patient prematurely discontinues treatment. These measurements will be allocated to a scheduled visit using the same criteria described above.

Pre-rescue therapy visit is entered in the eCRF if a patient receives rescue therapy. These measurements will also be allocated to a scheduled visit using the same criteria described above.

Furthermore, end of treatment visit measurements from patients prematurely discontinue the study (“Subject Status” in “Completion of End of Study/Follow-up” page is not “Completed”) will also be allocated to a scheduled visit using the same criteria described above.

Similar criteria of allocating an unscheduled measurement to a scheduled visit will be used for safety variables (laboratory variables, vital sign, ECGs, holter monitor variables), including measurements from premature treatment discontinuation visit, pre-rescue therapy visit, and end of treatment visit for patients prematurely discontinue the study if any. However, descriptive statistics, PCSA analyses, and shift summaries for safety variables are based only on data from TEAE period, a detailed definition of the TEAE period is provided in [Section 2.1.4](#).

After allocation, if there is still no measurement for a given parameter at a scheduled visit, multiple imputation would be applied efficacy and PRO questionnaires as described in [Section 2.4.4](#) and [Section 2.4.9](#).

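### The by-time-point SMPG rule omits the one-week limit and conflicts with Table 4, so an off-schedule reading up to 84 days old can count as Week 26 and escape imputation

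*SAP*

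**What the plan says.** Protocol Section 9.2.1.2.3 asks for the 7-point profile "over a single 24-hour period in the week before Visit 4 (Week 0), Visit 10 (Week 14), and Visit 12", the last being the Week 26 visit. No SMPG profile is routinely scheduled between Week 14 and the week before Week 26. SAP Section 2.1.3.2 analyses the mean daily value and adds that "the change from baseline to Week 26 for each of the 7 points will be evaluated, respectively".

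SAP Section 2.5.3 gives two selection rules in consecutive paragraphs:

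- **Daily mean.** Only values taken after the previous SMPG visit and "within a week of the next visit with scheduled 7-point SMPG measurements will be used to choose a SMPG profile" are eligible.
- **Each time-point.** The paragraph opens by saying that "a similar principal will be applied in selecting the data for analysis". In the working sentence a candidate need only have been obtained after the preceding SMPG visit. Of the readings that qualify, the one "closest to the next visit with scheduled 7-point SMPG measurements will be selected for the by time-point analysis". The sentence repeats the lower bound but not the week.

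SAP Section 2.5.4 has a third rule, for efficacy data in general. Table 4 allocates unscheduled values to visits by study day, and the text applies it to premature-discontinuation, pre-rescue and early end-of-treatment visits as well. Imputation comes last: "After allocation, if there is still no measurement for a given parameter at a scheduled visit, multiple imputation would be applied" to efficacy variables. For continuous secondary endpoints that is the placebo control-based method of Sections 2.4.4.1 and 2.4.4.2.

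**The concern.** Choosing the closest reading ranks the candidates but sets no maximum distance. A programmer who follows the by-time-point sentence literally would accept any reading taken after the Week 14 visit as the Week 26 value if nothing later exists. That value then counts as observed, so it is not imputed.

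Two things are at stake. First, the two parts of one secondary endpoint can treat the same patient differently: imputed from placebo for the daily mean, observed for a single time-point. Second, the plan deliberately gives active-arm patients without a Week 26 value a placebo-like outcome. An older reading taken on drug restores drug effect that the plan means to withhold. In the placebo group imputation already draws on placebo data, so there is no matching shift.

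Such readings have a planned source. At permanent discontinuation of study drug, and before rescue therapy, the protocol asks for the Visit 12 assessments (flow chart, note a; Section 8.8.2). These include the 7-point profile.

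**Working it through.** **Inputs.** SMPG visits at Weeks 0, 14 and 26 (Protocol 9.2.1.2.3). Target days and allocation ranges (SAP Table 4). Visit window of ±5 days from Visit 10 to Visit 12 (Protocol 10.1).

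**Target days reproduced.** 7 × 14 = 98 and 7 × 26 = 182, as in Table 4.

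**How old a Week 26 value may be under each rule:**

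| Rule | Earliest day counted as Week 26 | Days before day 182 |
|---|---|---|
| Daily mean (2.5.3) | 182 − 7 = 175 | 7 |
| Table 4 (2.5.4) | 161 | 182 − 161 = 21 |
| By time-point (2.5.3), read literally | after day 98 | up to 182 − 98 = 84 (12 weeks) |

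With both visits at the edges of their windows, the last figure becomes (182 + 5) − (98 − 5) = 94 days, or 13.4 weeks. No two of the three rules agree. Readings on days 161 to 174 are Week 26 under Table 4 but too old for the daily mean.

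**One patient through all three.** Take a single off-schedule reading on day 7 × 15 = 105, with no later reading:

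- Daily mean: 182 − 105 = 77 days, more than 7, so Week 26 is missing and is imputed.
- Table 4: days 77–118 belong to Visit 10, so Week 26 is missing and is imputed.
- By time-point: day 105 is after day 98 and no reading is closer, so it becomes the Week 26 value and is not imputed.

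**Who is affected.** A patient needs both no reading at the time-point in the week before Week 26 and an off-schedule reading after Week 14. The documents give no count of either.

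**Illustration only (assumptions, not in the documents).** Let a share m of an active arm be affected. Suppose that each such patient has an older reading showing the full on-drug effect D, and that imputation gives them zero effect. The arm's estimate is then (1 − m)D with imputation and D with the older readings. The relative overstatement is m/(1 − m):

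- m = 5%: 0.05/0.95 = 5%
- m = 10%: 0.10/0.90 = 11%
- m = 20%: 0.20/0.80 = 25%
- m = 30%: 0.30/0.70 = 43%

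These are upper bounds, because every assumption is set to its extreme.

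**The case against.** The strongest reply is Table 4. It covers efficacy data without exempting SMPG, and it would place a day-105 reading at Week 14. On that view the 84-day window never operates. This part stands: the literal outcome requires the SMPG paragraph to override Table 4, and no text says that it does. Equally, no text says that Table 4 overrides the SMPG paragraph, which is the more specific rule. The reply therefore turns the point into an unresolved conflict but does not remove it.

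Secondly, the linking phrase about a similar principle may have been meant to carry the week over, with the closest value then chosen inside that window. That is possible. But the sentence restates one condition and changes the other, so the intent is not recoverable from the text.

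Thirdly, the rule has no clear anchor when Visit 12 never takes place. If an early end-of-treatment visit at Week 16 counts as the next SMPG visit, a Week 15 reading is about a week from it and might qualify for the daily mean too. This stands, and the fix has to settle it.

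Two stronger readings are tempting but unsupported:

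- A reader might infer last-observation-carried-forward for dropouts in general. The value must come after the previous SMPG visit, so the scheduled Week 14 profile cannot be carried forward. A dropout with only scheduled data is imputed under every rule.
- A reader might infer a quantified bias, for instance 0.10 × 20 = 2 to 0.15 × 40 = 6 mg/dL. Neither the 10–15% share nor the 20–40 mg/dL effect is in the documents. Patients who stop study drug are followed to Week 26 and their values are used, so stopping drug is not the same as lacking a Week 26 value.

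**Conclusion.** The point holds as a gap and a conflict in the rules. The by-time-point sentence lacks the week that governs the daily mean, and it disagrees with Table 4 without stated precedence. Read literally, it lets an off-schedule value up to 84 days before Week 26 replace an imputed one.

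The number of patients affected is unknown, and the size of the effect cannot be derived from the documents. The likely direction is towards the active arms, assuming that the older readings were taken on drug with some effect present. It is not certain: a pre-rescue profile is taken when control is poor, and need not look better than a placebo-based imputation.

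The reach is one part of one secondary endpoint, with no trend test (SAP 2.4.4.2) and no multiplicity control (SAP 2.4.4.3). HbA1c, body weight and the hierarchical tests are unaffected. It should be corrected because the rule can give a wrong Week 26 value and the correction is nearly free.

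**What to change.** In SAP Section 2.5.3, limit the by-time-point sentence to readings that are also within a week of the scheduled SMPG visit, as for the daily mean. State in addition that:

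- when the visit does not take place, the week is measured from the targeted study day (day 182 for Week 26);
- this rule takes precedence over Table 4 for SMPG;
- older readings are treated as missing, so that at Week 26 they go to the control-based multiple imputation.

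The cost is a clause and a precedence statement in the SAP, and about one line of code, before database lock. The downside is that a few more values become missing. The oldest reading that can count as Week 26 falls from 84 days to 7 before the visit, and both parts of the endpoint then follow one missing-data rule.
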